9.4 Demographics and Baseline Characteristics

Descriptive statistics will be presented for baseline demographic, medical history, and procedural data on the randomized subjects. Data will be presented by group.

9.5 Analysis of Study Outcomes

9.5.1 Primary Outcomes

The primary outcome of difference in healing rates between groups will be assessed under the following hypothesis:

$$H_0: \pi_T - \pi_C \leq 0$$

$$H_a: \pi_T - \pi_C > 0$$

Where π_T is the healing rate at six months in the treatment group (RCR + DAA) and π_C is healing rate in the control group (non-augmented RCR) at six months. The difference in rates between groups will be summarized, along with a 95% confidence interval.

A chi-square test will be performed to obtain a p-value of the comparisons between groups. A one-sided p-value of <0.025 will be used to define success of the hypothesis (i.e., postoperative healing is improved with the addition of DAA).

9.5.2 Secondary Outcomes

The following secondary outcomes will be assessed using descriptive statistics, with results presented by group at Pre-op/Baseline and each follow-up.

- American Shoulder and Elbow Surgeons Score (ASES)
- Single Assessment Numeric Evaluation score (SANE)
- Visual Analog Scale (VAS) for pain
- Veterans RAND Health Survey (VR-12)

Changes from pre-operative values will also be summarized by group. Changes between groups may be compared using two-sample t-tests.

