3 STUDY DESIGN

3.1 Study Design and Rationale

This is a prospective randomized study comparing the outcomes of patients undergoing rotator cuff repair with dermal allograft augmentation (DAA) or a control group without dermal allograft. Patient outcomes will be collected and compared between the two cohorts at two years postoperative and will include a range of subjective and functional outcomes and radiographic imaging. All patients undergoing primary rotator cuff repair surgery will be invited to be part of the study after pre-operative inclusion/exclusion criteria have been met.

Hypothesis: Patients undergoing rotator cuff repair surgery will experience improved tendon healing with the use of CuffMend™ dermal allograft augmentation.

The purpose of this study is to compare postoperative healing of large and massive rotator cuff tears with preoperative MRI confirmed fatty infiltration stage II and higher repaired with or without dermal allograft augmentation (DAA).

The outcome measures were selected based on the recommendations of the American Academy of Orthopaedic Surgeons (AAOS) and literature review.

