3.3 Study Objectives and Outcome Measures

3.3.1 Study Objectives

The purpose of this study is to compare postoperative healing of large and massive rotator cuff tears with preoperative fatty infiltration stage II and higher repaired with or without DAA.

Primary Hypothesis: Improved postoperative healing with the addition of CuffMend™ DAA, assessed with MRI Imaging

Secondary Hypothesis: Improved Patient-Reported Outcomes and range of motion with the addition of CuffMend™ DAA

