3.4 Study Outcome Measures

The primary outcome measure is the healing rate in MRI.

- MRI Post-Operative Assessment (Goutallier Stage and Sugaya Classification)

The secondary outcomes measures patient-reported outcomes from validated outcome scoring systems and range of motion objective measures.

- American Shoulder and Elbow Surgeons Score (ASES)
- Single Assessment Numeric Evaluation score (SANE)
- Visual Analog Scale (VAS) for pain
- Veterans RAND Health Survey (VR-12)
- ASES Objective Shoulder Assessment (ROM)

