9 STATISTICAL CONSIDERATIONS

The study is a post-market clinical follow-up study. Given the observational nature of the study a sample size calculation was not performed. The total enrollment goal of 120 subjects was selected in an effort to create a generalizable sample that is large enough to provide sufficient data on safety and performance. Outcomes recorded at specific time points will be analyzed according to standard measures of descriptive statistics. The number of dropouts and withdrawals will be presented. Interim analyses may be conducted based on regulatory request. After completion of the study, a final report encompassing all study data will be generated.

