9.2 Descriptive Statistics

Continuous data will be summarized with mean, standard deviation, median, minimum, maximum, and number of evaluable observations. Categorical data will be summarized with frequency counts and percentages. Confidence intervals may be presented, where appropriate, using the t-distribution for continuous data and normal approximation for binomial data (unless otherwise noted).

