9.5.3 Objective Outcomes

Shoulder range of motion (ROM) in forward flexion, external and internal rotation will be summarized by group at 26 weeks and one year, along with the changes from Pre-op/Baseline to each time point.

Post-operative cuff integrity is determined through MRI and is classified into five categories, as described by Sugaya et al.¹⁰ type I, sufficient thickness with homogeneously low intensity; type II, sufficient thickness with partial high intensity; type III, insufficient thickness without discontinuity; type IV, presence of a minor discontinuity; type V, presence of a major discontinuity. Data will be summarized by group using frequency distributions.

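### The secondary hypothesis is a between-group claim that section 9 does not carry through; ANCOVA on the baselines already scheduled would supply the comparison, possibly with better precision, at no cost in patients

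*Combined protocol and SAP*

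**What the plan says.** **The promise of a comparison.** Section 3.3.1 gives the secondary hypothesis as "Improved Patient-Reported Outcomes and range of motion with the addition of CuffMend™ DAA". Section 3.4 counts ROM among the secondary outcomes: "The secondary outcomes measures patient-reported outcomes from validated outcome scoring systems and range of motion objective measures". Section 3.1 adds a time: "Patient outcomes will be collected and compared between the two cohorts at two years postoperative".

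**The analysis.** Section 9 opens with a general statement: "Outcomes recorded at specific time points will be analyzed according to standard measures of descriptive statistics". Section 9.5.2 covers ASES, SANE, VAS and VR-12 descriptively, "with results presented by group at Pre-op/Baseline and each follow-up", then adds that "Changes between groups may be compared using two-sample t-tests". It names no visit, significance level, estimate or multiplicity rule. Section 9.5.3 says that ROM "will be summarized by group at 26 weeks and one year, along with the changes from Pre-op/Baseline to each time point", and gives no difference, interval or test between groups.

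**The data.** The section 6 schedule marks ASES, VAS, VR-12, SANE and ROM at the pre-operative visit. After surgery, ASES, SANE and VR-12 are collected at 26 weeks, one year and two years. VAS is collected at those visits and also at two and six weeks. ROM is collected at 26 weeks and one year only.

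**The concern.** The secondary hypothesis has no committed analysis. Section 3.1 names two years, but without a method, and section 9 does not repeat it. As section 9 stands, whether PROs are tested at all, and which score and visit are put forward, could be settled once the data are known. For ROM the plan has no between-group comparison, and section 3.1 names a visit at which ROM is not measured.

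The one method named is also not the most efficient use of the data. Subtracting the baseline fixes its coefficient at 1. ANCOVA estimates the coefficient from the same pairs of values and allows for a chance baseline difference between the arms. At stake is the width of the intervals on the secondary outcomes and how clearly they can be read. The primary result is not at stake.

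**Working it through.** **1. Patients per arm.** Section 9.1 assumes healing of 75% against 40%, one-sided alpha 0.025 and 90% power. The pooled Z-test formula gives

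n = [1.96·√(2·0.575·0.425) + 1.2816·√(0.75·0.25 + 0.40·0.60)]² / 0.35² ≈ 39.8, so 40 per group.

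Allowing for 33% dropout, 40/0.67 = 59.7, so 60 per group. Both of the plan's figures are reproduced. They size the six-month MRI endpoint; 40 per arm at two years is an assumption.

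**2. Number of secondary comparisons** (VR-12 counted as one score).
- PROs: 3 scores × 3 visits + VAS × 5 visits = 14.
- ROM: 4 goniometer measures × 2 visits = 8.
- Expected false positives at two-sided 5% with no effect, whatever the correlation between tests: 14 × 0.05 = 0.7 for PROs; 22 × 0.05 = 1.1 for all.

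**3. Variance.** Let r be the correlation between baseline and follow-up, and k the follow-up SD divided by the baseline SD. The documents give neither, so both are assumed. In units of the squared baseline SD:
- change score: 1 + k² − 2rk
- ANCOVA: k²(1 − r²) × [1 + 1/(2n − 4)]; the bracket is the cost of estimating one coefficient, 1 + 1/76 = 1.013 at n = 40 per arm.

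Example with k = 1 and r = 0.5: change score 1.00; ANCOVA 0.75 × 1.013 = 0.760; variance falls by 24%.

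Ratio of ANCOVA variance to change-score variance, 40 per arm:

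| k | r = 0.3 | r = 0.5 | r = 0.7 |
|---|---|---|---|
| 0.67 | 0.395 | 0.438 | 0.454 |
| 1 | 0.659 | 0.760 | 0.861 |
| 1.25 | 0.795 | 0.905 | 0.994 |
| 1.5 | 0.883 | 0.977 | 1.011 |

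**4. What this means for intervals and power.** With k = 1 and 40 per arm, the 95% CI half-width in follow-up SDs goes from 0.527, 0.445, 0.345 (change score; r = 0.3, 0.5, 0.7) to 0.428, 0.388, 0.320 (ANCOVA).

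Power at two-sided 5% for an assumed difference of 0.5 follow-up SD, 40 per arm:

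| Analysis | r = 0.3 | r = 0.5 | r = 0.7 |
|---|---|---|---|
| Change score, k = 0.67 | 30% | 39% | 54% |
| Change score, k = 1 | 46% | 60% | 81% |
| Change score, k = 1.5 | 58% | 71% | 87% |
| ANCOVA, any k | 63% | 72% | 87% |

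Simulation with 20,000 trials per cell (k = 0.67, 1 and 1.5; 40 and 60 per arm) agreed with the calculated power to within 0.01. With no effect, both tests rejected in 4.8% to 5.4% of trials, so both are valid.

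**5. Chance imbalance.** At 40 per arm the SD of the baseline mean difference is √(2/40) = 0.224 SD. With k = 1, an imbalance of that size shifts the change-score estimate by (1 − r) × 0.224 = 0.157, 0.112 or 0.067 SD. ANCOVA removes this shift.

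**The case against.** **Description may be deliberate.** Section 9 plans descriptive statistics, only the primary outcome has a success rule, and section 9.2 says that "Confidence intervals may be presented, where appropriate, using the t-distribution for continuous data". A reader could work out an unadjusted difference from the by-group summaries. All of this is true, and a secondary hypothesis needs no power target. But a plan that only describes does not match the comparison promised in sections 3.1 and 3.3.1. One side has to be changed.

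**A visit is named.** A reader of section 9 alone might infer that no key visit exists. The documents do not support that, because section 3.1 says two years. What stands is narrower: section 9 does not take it up, and it cannot apply to ROM.

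**The t-test is not wrong.** A reader might infer that change-score t-tests are biased or invalid. Under randomisation they are valid. The choice is one of efficiency.

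**The gain rests on assumed inputs.** It does. Over the grid shown it runs from a variance reduction of about 60% to a loss of 1%, and nothing in the documents says where each measure falls. Two-year numbers could also be below 40 per arm, since section 4.3 does not replace patients withdrawn after treatment.

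**The remedy adds tests.** Fourteen optional PRO comparisons become 22 planned ones, and four PROs remain co-equal at two years. This is a fair point. The answer is an explicit exploratory label with the expected count stated, not a claim that multiplicity is controlled.

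**Conclusion.** The concern holds as a mismatch between the secondary hypothesis and its analysis, together with an improvement that costs nothing. It is not an error that threatens the trial. The mismatch rests on the text alone and needs no assumption.

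The precision gain is possible but not established. With 40 per arm and equal SDs, variance falls by about 34%, 24% and 14% at r = 0.3, 0.5 and 0.7. The gain is larger if the follow-up SD is below the baseline SD. At 1.5 times baseline it is small or nil, or a 1% loss at r = 0.7. In large samples ANCOVA is never less efficient than the change score, so the downside is limited to the cost of one coefficient. These figures depend on assumed values of r, k and two-year numbers.

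It would be tempting to read this as casting doubt on the healing comparison or the sample size. It does neither: the primary chi-square test, its one-sided 0.025 rule and the total of 120 are untouched.

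**What to change.** - **Section 9.5.2:** replace the optional t-test sentence with a commitment such as: *ASES, SANE, VAS and VR-12 will each be compared by ANCOVA of the follow-up score on arm and the pre-operative value of the same score, reporting the adjusted difference and 95% CI. Two years is the key visit; earlier visits are supportive.*
- **Section 9.5.3:** use the same model for the four goniometer ROM measures at 26 weeks and one year, with one year as the key visit. Internal rotation by spinal level can stay descriptive.
- **Section 3.1:** state that ROM is compared at one year.
- **Section 9, opening paragraph:** make the descriptive-statistics sentence refer to 9.5 for between-group comparisons.
- **Multiplicity:** state that all secondary comparisons are exploratory with no multiplicity control, and that 14 PRO and 8 ROM comparisons would give about 1.1 expected false positives at two-sided 5% if there were no effect.

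If description alone is intended, reword sections 3.1 and 3.3.1 so that they do not promise a comparison of these outcomes.

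The cost is a few sentences of wording and standard software. There are no new visits, data or patients. A change score already needs the same baseline and follow-up pair, so ANCOVA uses the same patients and fits the no-imputation rule in section 9.3.

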9.5.3 Objective Outcomes

Shoulder range of motion (ROM) in forward flexion, external and internal rotation will be summarized by group at 26 weeks and one year, along with the changes from Pre-op/Baseline to each time point.

Post-operative cuff integrity is determined through MRI and is classified into five categories, as described by Sugaya et al.¹⁰ type I, sufficient thickness with homogeneously low intensity; type II, sufficient thickness with partial high intensity; type III, insufficient thickness without discontinuity; type IV, presence of a minor discontinuity; type V, presence of a major discontinuity. Data will be summarized by group using frequency distributions.

10 ETHICS/PROTECTION OF HUMAN SUBJECTS

10.1 Ethical Standards and Guidelines

The investigator will ensure that this study is conducted in full conformity with the protocol and the fundamental principles set forth in Declaration of Helsinki and ISO 14155, as far as relevant.

10.2 Institutional Review Board/ Ethics Committee

The protocol, informed consent form(s), recruitment materials, and all subject materials will be submitted to the IRB/EC for review and approval. Approval of both the protocol and the consent form must be obtained before any subject is enrolled. Any amendment,

to the protocol will be reviewed and approved by the IRB/EC per the IRB/EC guidelines. All written and dated approvals from the IRB/EC shall be retained by the Site and Sponsor.

10.3 Informed Consent Process

Informed consent is a process that is initiated prior to the individual agreeing to participate in the study and continues throughout study participation. Extensive discussion of the risks and possible benefits of study participation will be provided to subjects and their families, if applicable. A consent form describing in detail the study procedures and risks will be given to the subject.

Consent forms will be IRB/EC-approved, and the subject is given ample time to read and review the document. The investigator or designee will explain the research study to the subject and answer any questions that may arise. The investigator or designee will ensure that the subject's participation is voluntary, and no coercion to enroll in the study has occurred. The subject will sign the informed consent document prior to any study-related assessments or procedures. Subjects will be given the opportunity to discuss the study with their surrogates or think about it prior to agreeing to participate. They may withdraw consent at any time throughout the course of the study without prejudice to their medical care. The informed consent process will be documented in the source documents. A copy of the signed and dated informed consent document will be given to subjects for their records. The subject will be updated with any new study information that may affect their willingness to participate. The rights and welfare of the subjects will be protected by emphasizing to them that the quality of their clinical care will not be adversely affected if they decline to participate in this study.

10.4 Subject Confidentiality

Subject confidentiality is strictly held in trust by the investigators, site staff, and the sponsor(s) and their agents. This confidentiality is extended to cover testing of biological samples and genetic tests in addition to any study information relating to subjects.

The study protocol, documentation, data, and all other information generated will be held in strict confidence. No information concerning the study, or the data will be released to any unauthorized third party without prior written approval of the sponsor.

The study monitor or other representatives of the sponsor may inspect all study documents and records required to be maintained by the investigator, including but not limited to, medical records (office, clinic, or hospital) for the study subjects. The clinical study site will permit access to such records.

11 DATA HANDLING AND RECORD KEEPING

11.1 Data Management Responsibilities

The investigators are responsible for ensuring the accuracy, completeness, legibility, and timeliness of the data reported. All source documents should be completed in a neat, legible manner to ensure accurate interpretation of data. The investigators will maintain adequate case histories of study subjects, including accurate case report forms (CRFs), and source documentation. Site staff shall ensure any change or correction reported on a CRF shall be dated, initialed, and explained if necessary, and shall not obscure the original entry. Site staff will maintain appropriate medical and research records for this study. Site staff will permit authorized representatives of Arthrex to examine research records for the purposes of quality assurance reviews, audits, and evaluation of the study safety, progress, and data validity.

Data collection and accurate documentation are the responsibility of the site staff under the supervision of the investigator. All source documents must be reviewed by the study team and data entry staff, who will ensure that they are accurate and complete.

The sponsor will have procedures in place for system validation for the EDC. The sponsor shall periodically remotely review data and send queries to the site for missing or erroneous data. eCRF completion guidelines will be given to the site and are maintain separate from the protocol. If an amendment of the protocol occurs, CRFs will be updated as appropriate and applicable. The eCRFs shall be signed and dated by the Principal Investigator or authorized designee prior to site closeout.

11.2 Data Capture Methods

Data will be entered into a password protected EDC system by the site staff. The data may be collected on paper source worksheets or from the medical record. The sponsor should use an unambiguous subject identification code that allows identification of all the data reported for each Subject. The link between the code and each Subject shall be retained by the PI in a secure location. Subject questionnaires may be entered directly into the EDC by the subject. All data shall be entered into the EDC in a timely manner. De-identified images (MRIs) will be stored separately from the EDC, in a DICOM system for the study.

11.3 Study Records Retention

At the site, study records will be maintained for at least three years from date of study completion. No records will be destroyed without the written consent of the sponsor. The

Sponsor and PI shall retain all study documents and shall take action to ensure no accidental or premature destruction of these documents occurs. The PI and Sponsor may transfer custody of records to another person or party and document the transfer.

11.4 Protocol Deviations

A protocol deviation is any noncompliance with the clinical study protocol, ethical standards, or regulations. Investigators shall not deviate from the protocol except to protect the rights or well-being of a subject. Significant deviations will be reported to Arthrex in a timely manner and to the IRB/EC per their guidelines.

11.5 Amendments to the Protocol

Protocol amendments will be completed by Arthrex. At each protocol amendment all appendices and supporting documents will be reviewed for impact and updated as appropriate. Arthrex will notify all active sites of each protocol amendment for submission to the IRB/EC as necessary per the IRB/EC guidelines.

12 STUDY CLOSE OUT

The completion of a clinical study shall be deemed to coincide with the final database lock, whether or not the clinical study concluded according to the pre-specified study closeout activities or was terminated prematurely.

After study close out, a report of the clinical study shall be completed, even if terminated prematurely. The report shall be in written form, and include identification of the device(s), a description of the methodology and design of the clinical study, deviations from the Protocol, data analysis and statistics, and critical appraisal of the results compared to the objectives of the clinical study.

The results of the clinical study shall be entered in a publicly accessible database where the clinical study was registered, such as clinicaltrials.gov, and published whether positive, inconclusive, or negative to help guide future research device development and medical treatment.

13 PUBLICATION/DATA SHARING POLICY

The clinical study will be registered in a publicly accessible database, as appropriate to the study location guidelines.

Publication rights, criteria for authorship, conditions and time frames for publication are defined in the site clinical trial agreement.

These documents are relevant to the protocol, but they are not considered part of the protocol. They are stored and modified separately. As such, modifications to these documents do not require protocol amendments.

- Site Roster
- Key Sponsor Personnel
- CRF Completion Guidelines
- Case Report Forms

APPENDICES

- Appendix 1: Key Study Questionnaires
- Appendix 2: Consent Form Template
